12 APPENDIX 2: SUBSCALE SCORES AND TOTAL SCORES FOR INQOL QUESTIONNAIRE

Subscale scores and total scores for INQoL questionnaire will be calculated with the following rules.

Dimensions	Subscales	Number of Items	Cluster of Items
Section 1: Symptoms	Weakness	3	1 a, b, c
	Pain	3	2 a, b, c
	Feeling Tired	3	3 a, b, c
	Locking	3	4 a, b, c
	Droopy eyelids	3	5 a, b, c
	Double vision	3	6 a, b, c
	Swallowing	3	7 a, b, c
Section 2: Life domains	Activities	5	1 AI, II, III 1 BI, II
	Independence	3	2 A, 2 BI, 2 BII
	Social relationship	10	3 AI, II, III, IV 3 BI, II, III, IV, V, VI
	Emotions	6	4 AI, II, III, IV 4 BI, II
	Body image	3	5 A, 5 BI, II
Section 3: Treatment Effects	Perceived treatment effects	3	1 AI, III 1 BI, III
	Expected treatment effects	3	1 AII, III 1 BII, III
Quality of life		14	Items from section B for questions on section 2.

Calculating individual scores:

1. **Weakness score** = $(a+b+c) / 19 \times 100$

Worldwide Clinical Trials Controlled Quality Management Document

Sponsor: PTC Therapeutics, Inc

Protocol Number: PTCEMF-GD-004

STATISTICAL ANALYSIS PLAN

2. **Pain score** = $(a+b+c) / 19 \times 100$
3. **Feeling tired score** = $(a+b+c) / 19 \times 100$
4. **Muscle locking score** = $(a+b+c) / 19 \times 100$
5. **Droopy eyelids score** = $(a+b+c) / 19 \times 100$
6. **Double vision score** = $(a+b+c) / 19 \times 100$
7. **Swallowing score** = $(a+b+c) / 19 \times 100$
8. **Activities score** = $[4 \times (AI+AII+AIII)] + [3 \times (BI+BII)] / 108 \times 100$
If not working due to condition item -> AIII=6
If retired/unemployed/work in home (not as a result of condition)
-> $[6 \times (AI+AII)] + [3 \times (BI+BII)] / 108 \times 100$
9. **Independence score** = $[12 \times A] + [3 \times (BI+BII)] / 108 \times 100$
10. **Social relationships** = $[3 \times (AI+AII+AIII+AIV)] + [BI+II+III+IV+V+VI] / 108 \times 100$
If partner/spouse item (AI) not applicable:
-> $[4 \times (AII+AIII+AIV)] + [BI+II+III+IV+V+VI] / 108 \times 100$
11. **Emotions score** = $[3 \times (AI+AII+AIII+AIV)] + [3 \times (BI+BII)] / 108 \times 100$
12. **Body Image score** = $[12 \times (A)] + [3 \times (BI+BII)] / 108 \times 100$
13. **Perceived treatment effect score** = $[(AI+AIII)-(BI+BIII)]/12 \times 100$
14. **Expected treatment effect score** = $[(AII+AIII)-(BII+BIII)]/12 \times 100$
15. **QoL score**: Add scores of items in section B for questions on section 2 (with correction i.e. 3X (BI + B2) for Quns 1,2,4&5 and BI+II+III+IV+V+VI for Qun 3), divide total score by 180 and multiply by 100 (to achieve percentage score)

Handling missing observations:

Section 1:

Q1-7

QMD Ref: Worldwide-TMP-ST-005-7.0 Effective: 12Aug2019

Governing QMD: Worldwide-SOP-ST-001

Confidentiality Statement

This document is the property of Worldwide Clinical Trials Inc. and may not be duplicated, copied, altered or removed from company without prior approval from Worldwide Quality Assurance or in compliance with Worldwide Standard Operating Procedures.

Worldwide Clinical Trials Controlled Quality Management Document		
 WORLDWIDE CLINICAL TRIALS	Sponsor:	PTC Therapeutics, Inc
	Protocol Number:	PTCEMF-GD-004
STATISTICAL ANALYSIS PLAN		

1A-4A If missing and rest of symptom qun missing (i.e. part B) -> score zero

1B-4B a. If missing, score “1”

b. If missing, impute previous value (part a)

c. If missing, score “0”

Section 2:

Q1

1 A. If an item missing, sum completed items, and multiply by 6 if two items completed and 12 if only one item has been completed (to get score out of 72)

(N.B. “Work activities” item: if not working due to condition score “6” and count as a completed item).

EXAMPLE: If “Leisure activities” is missing, add values of “Daily activities” & “Work Activities”. Multiply this by 6.

BI. If missing, impute average of completed “activities” items (from 5A)

BII. If missing, score as “0”

Q2

2 A. if missing, score as “0”

BI. If missing, impute value from 2A

BII. If missing, score as “0”

Q3

3 A. If item missing, sum the completed items and multiply by 4 if three completed items, 6 if two completed items & 12 if one completed item

BI. If missing, impute average of 3a items

i) Relationship with spouse/partner &

ii) Relationship with other family members

BII. If missing, score as “0”

QMD Ref: Worldwide-TMP-ST-005-7.0 Effective: 12Aug2019	Governing QMD: Worldwide-SOP-ST-001
Confidentiality Statement	
This document is the property of Worldwide Clinical Trials Inc. and may not be duplicated, copied, altered or removed from company without prior approval from Worldwide Quality Assurance or in compliance with Worldwide Standard Operating Procedures.	

Worldwide Clinical Trials Controlled Quality Management Document		
 WORLDWIDE CLINICAL TRIALS	Sponsor:	PTC Therapeutics, Inc
	Protocol Number:	PTCEMF-GD-004
STATISTICAL ANALYSIS PLAN		

BIII. If missing, impute value from “Friends” (3AII) item

BIV. If missing, score as “0”

BV. If missing, impute value from “Other people” (3AIV) item

BVI. If missing, score as “0”

Q4

4 A. If item missing, sum the completed items and multiply by 4 if three completed items, 6 if two completed items and 12 if one completed item

BI. If missing, impute average of items completed in 4A

BII. If missing, score as “0”

Q5

A. If missing, score as “0”

BI. If missing, impute value from 5A

BII. If missing, score as “0”

Section 3:

Q1

1A I. If missing, score as “0”

II. If missing, score as “0”

III. If missing, score as “0”

1B I. If missing, score as “0”

II. If missing, score as “0”

III. If missing, score as “0”

QMD Ref: Worldwide-TMP-ST-005-7.0 Effective: 12Aug2019	Governing QMD: Worldwide-SOP-ST-001
Confidentiality Statement	
This document is the property of Worldwide Clinical Trials Inc. and may not be duplicated, copied, altered or removed from company without prior approval from Worldwide Quality Assurance or in compliance with Worldwide Standard Operating Procedures.	

Certificate Of Completion

Envelope Id: [REDACTED] Status: Completed
Subject: Please DocuSign: PTCEMF-GD-004 SAP v1.0.pdf
Source Envelope:
Document Pages: 32 Signatures: 6 Envelope Originator:
Certificate Pages: 6 Initials: 0 [REDACTED]
AutoNav: Enabled [name]
Enveloped Stamping: Disabled [name]
Time Zone: (UTC-06:00) Central Time (US & Canada) [name]
[REDACTED]
IP Address: [REDACTED]

Record Tracking

Status: Original Holder: [REDACTED] Location: DocuSign
04-Nov-2020 | 01:41

Signer Events

[REDACTED]
Security Level: Email, Account Authentication
(Required)

Signature

[REDACTED]
Signature Adoption: Pre-selected Style
Signature ID:
[REDACTED]
Using IP Address: [REDACTED]

Timestamp

Sent: 04-Nov-2020 | 02:09
Viewed: 04-Nov-2020 | 09:18
Signed: 04-Nov-2020 | 09:23

With Signing Authentication via DocuSign password
With Signing Reasons (on each tab):
I approve this document

Electronic Record and Signature Disclosure:
Not Offered via DocuSign

[REDACTED]
Security Level: Email, Account Authentication
(Required)

[REDACTED]
Signature Adoption: Pre-selected Style
Signature ID:
[REDACTED]
Using IP Address: [REDACTED]

Sent: 04-Nov-2020 | 02:09
Viewed: 04-Nov-2020 | 07:32
Signed: 04-Nov-2020 | 07:33

With Signing Authentication via DocuSign password
With Signing Reasons (on each tab):
I approve this document

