### **Study assessments**

In this study, muscle function following deflazacort or placebo therapy will be evaluated using a number of tests that assessed different aspects of muscle function, such as peak physical activity

(timed-function tests), endurance (2-minute walk test), muscle strength (myometry), and pulmonary function (FVC, MIP, and MEP).

The PK of deflazacort will be investigated to evaluate the exposure of the drug in subjects with LGMD2I; a population in which this assessment has not been previously performed. This information may help to determine the relationship of drug exposure with the efficacy and safety of the drug in this patient population. The following PK parameters will be calculated using noncompartmental analysis method:  $AUC_{(0-t)}$ ,  $AUC_{(0-inf)}$ ,  $C_{max}$ ,  $T_{max}$ ,  $CL/F$ ,  $Vz/F$ ,  $\lambda_z$ , and  $t_{1/2}$ .

Magnetic resonance imaging (specifically Dixon MRI and global T2) are noninvasive methods that will be used to measure changes in muscular fat fraction and water content, respectively, of the muscle following deflazacort treatment. These methods have been shown to detect therapeutic effects of corticosteroids in reducing inflammatory processes in skeletal muscle of boys with DMD (Arpan 2014, Hathout 2016a). The advantage of the use of these potential biomarkers is that they are anticipated to be independent of muscle function, such as the ability to walk (Hathout 2016a).

The INQoL questionnaire, developed by Vincent et al. (2007), consists of 45 questions within 10 sections, 4 sections focus on the impact of key muscle disease symptoms (weakness, locking [ie, myotonia], pain, and fatigue), 5 sections focus on the impact of muscle disease on particular areas of life (activities, independence, social relationships, emotions, and body image), and 1 section asks about the positive and negative effects of treatment, reflecting the trade-off between the positive and negative effects of treatment now and in the future (Vincent 2007).

The life domains that emerged correspond to the broad domains believed to make up the QoL spectrum (physical, psychological, and social functioning). The questionnaire is structured to allow for variations in the individual characteristics that influence quality of life.

Participants respond using a 7-point Likert scale.

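### INQoL scoring in SAP Appendix 2 gives wrong scores if programmed as printed: seven formulas lack a bracket, one imputation rule cites the wrong domain, and one item label needs checking

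*SAP*

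**What the plan says.** SAP section 6.2.5 sends the reader to Appendix 2 for the INQoL calculation, so the appendix is what a programmer will code from.

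**Formulas.** Activities is printed as "4 \times (AI+AII+AIII)] + [3 \times (BI+BII)] / 108 \times 100" (one opening square bracket stands just before the quoted run). The other life-domain lines have the same shape: a weighted Part A in square brackets, plus a weighted Part B in square brackets, then a division by 108 and a multiplication by 100. Seven lines are written this way: Activities and its variant for subjects who are not working for reasons other than the condition, "Independence score", Social relationships and its no-partner variant, Emotions, and Body image. The symptom formulas (divided by 19) and the two treatment-effect formulas (divided by 12) do bracket the whole numerator. The QoL score is described in words and divides the total by 180.

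**Missing items.** For Activities the rule is "BI. If missing, impute average of completed “activities” items (from 5A". For Social relationships, BI is the average of two 3A items, spouse/partner and then "ii) Relationship with other family members"; the next rule reads "BIII. If missing, impute value from “Friends” (3AII) item"; and BV is taken from the other-people item, labelled 3AIV.

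**Use.** SAP section 6.10.3 presents INQoL results in by-subject listings only. SAP section 1 reports that 11 subjects were enrolled.

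**The concern.** The protocol (Study assessments) presents the INQoL score as a percentage of the maximum detrimental impact, so a value above 100 has no meaning. As printed, the life-domain formulas can produce one. More generally, they inflate every life-domain score in which Part A is above zero, whether or not any item is missing.

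The Activities imputation rule contradicts itself: its words name one set of items and its cross-reference names an item from another domain. The Friends rule carries a label that sits badly with the other labels in the same appendix.

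At stake is the accuracy of individual listed scores. With so few subjects and no summary table, a listed score may be read one subject at a time.

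**Working it through.** **Inputs**

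- Life-domain items run from 0 to 6. The protocol states "Participants respond using a 7-point Likert scale". The SAP sets the worst work answer to 6 ("If not working due to condition item -> AIII=6") and scores some missing items as zero. Its Part A rule ("multiply by 6 if two items completed and 12 if only one item has been completed (to get score out of 72") gives 12 × 6 = 72.
- Write A for the weighted Part A and B for the weighted Part B of a domain.

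**Step 1: reproduce the plan's denominators**

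| Formula line | Maximum A | Maximum B | Sum |
|---|---|---|---|
| Activities | 4 × 18 = 72 | 3 × 12 = 36 | 108 |
| Activities, not-working variant | 6 × 12 = 72 | 3 × 12 = 36 | 108 |
| Independence; Body image | 12 × 6 = 72 | 3 × 12 = 36 | 108 |
| Social relationships | 3 × 24 = 72 | 6 × 6 = 36 | 108 |
| Social, no-partner variant | 4 × 18 = 72 | 6 × 6 = 36 | 108 |
| Emotions | 3 × 24 = 72 | 3 × 12 = 36 | 108 |

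The QoL maximum is 4 × 36 + 36 = 180. Both 108 and 180 reproduce exactly. The 108 fits only if A and B are added before dividing.

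**Step 2: effect of the missing bracket**

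- Intended: (A + B)/108 × 100.
- As printed, with ordinary precedence: A + B/108 × 100.
- Difference: A − A × 100/108 = A × 8/108 = 0.0741 × A. At A = 72 this is 5.33 points.

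| Case | A | B | As printed | Intended |
|---|---|---|---|---|
| All items 6 | 72 | 36 | 72 + 33.33 = 105.33 | 100 |
| All items 3 | 36 | 18 | 36 + 16.67 = 52.67 | 50 |
| Near ceiling | 72 | 33 | 72 + 30.56 = 102.56 | 97.22 |
| Near ceiling | 68 | 36 | 68 + 33.33 = 101.33 | 96.30 |

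The first two rows hold in all five domains. Values above 100 are confined to the ceiling: 3 of the 247 possible (A, B) pairs for Activities, 2 of 91 for Independence and 9 of 925 for Social relationships. These are counts of combinations, not probabilities.

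**Step 3: Activities BI when missing**

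The table in Appendix 2 places activities in question 1 (1 AI to AIII) and gives question 5 to body image, with a single A item. The body-image rule later in the appendix also uses 5A in that sense. BI carries weight 3, so if the activities average and 5A lie at opposite extremes:

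- Activities: 3 × 6/108 = 16.7 points.
- QoL: 3 × 6/180 = 10.0 points.

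Example with the bracket restored: 1A items all 6, BI missing, BII = 6, 5A = 0. Following the label gives (72 + 18)/108 × 100 = 83.3; following the words gives (72 + 36)/108 × 100 = 100.

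**Step 4: Social BIII when missing**

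The appendix labels AI as partner/spouse and AIV as other people. That leaves AII and AIII for family and friends. Family is listed second, directly after the partner. The B rules also run in the order partner and family, friends, other people. Both facts suggest that family is AII and friends AIII. BIII carries weight 1, so at opposite extremes:

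- Social relationships: 6/108 = 5.6 points.
- QoL: 6/180 = 3.3 points.

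**The case against.** The intent can be recovered. Part A is stated to be out of 72, the denominators fit only a bracketed numerator, and the protocol defines a percentage of a maximum. Both imputation rules name the intended item in words, and an average of several activities items cannot come from a single body-image item. A careful programmer might therefore get all of this right. That argument lowers the likelihood of harm, but it does not make the printed rules correct.

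The formulas reached this review through PDF conversion, so a lost fraction layout cannot be fully excluded. Against that, the symptom and treatment-effect formulas nearby keep their outer brackets.

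Four stronger readings are tempting, and the documents do not support them:

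- **That the appendix itself labels family as AII.** It does not. The i) and ii) in the BI rule may only be list markers for the two items to be averaged. Friends as 3AII with family as 3AIII would be a coherent alternative, and the questionnaire is not in the documents. The label is doubtful, not proven wrong.
- **That both pointers bring in another domain's answer.** Only 5A does. Items 3AII and 3AIII both belong to Social relationships.
- **That scores above 100 would be common.** They need near-maximal answers. The general effect is a modest overstatement, mostly within 0 to 100.
- **That 16.7 and 5.6 points are typical errors.** They are ceilings. Each needs the particular item to be missing and two answers at opposite ends of the scale.

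The low stakes also stand. Protocol section 9.4 plans by-patient listings for each CRF module, so item responses should be available for recalculation.

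**Conclusion.** The point holds as a minor one. The formula lines and the 5A reference are wrong as printed; the 3AII label is probably wrong and needs checking.

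Taken literally, the bracket fault affects every life-domain score with a non-zero Part A. The two pointer faults act only when 1BI or 3BIII is missing, and they carry through to the QoL score. The bracket fault does not touch the symptom, treatment-effect or QoL formulas.

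This rests on 0-to-6 item scoring, ordinary operator precedence, brackets in the source document as they appear in the text, and listings that show derived scores and not only item responses. The effect is limited to exploratory by-subject listings in 11 subjects.

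**What to change.** - In all seven life-domain lines, bracket the whole numerator: ([Part A] + [Part B])/108 × 100.
- In the Activities BI rule, change the reference from 5A to 1A.
- Check the Friends label against the questionnaire and its scoring instructions, and change 3AII to 3AIII if that is confirmed.
- Test the scoring program on constructed records: all life-domain items at 6 should return 100 in each domain, and all at 3 should return 50. A 0-to-100 range check alone would miss most bracket errors, because most inflated scores stay below 100.

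The cost is seven formula edits, one reference edit and one conditional label edit in an appendix. Any INQoL listing already produced from the literal rules would need to be rerun. No other output is affected.
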